6.1 Screening

- Informed Consent
- Complete MRI Safety Screening Form & TSS form
- Medical History – patient self-report
- Clinician administered measures of mood, behavior and prior treatment history
 - MADRS
 - SCID

CONFIDENTIAL

This material is the property of the University of Pennsylvania.

- Test TMS with participant to ensure tolerability

6.2 Study Intervention Phase

6.2.1 MRI Visits

- Verify & sign MRI Safety Screening Form
- Undergo MRI with tasks
 - Baseline MRI – tasks in the scanner, no TMS probe
 - Visit 1 – tasks in the scanner with TMS

6.2.2 Prior to Baseline MRI – Randomized order of learning all 3 study tasks (SST, IAPS, and Sham) in the scanner without TMS.

6.2.3 Visit 1 – in the scanner participant completes all 3 tasks, in previously randomized order with TMS.

6.2.4 After Visit 1 – Randomized to SST task only, IAPS task only, or Sham task only & either Active rTMS + task or Sham rTMS + task

5.2.5 Neuromodulation & MRI Probe Visits:

- Visits 2 & 3: Complete randomized task alone & again with randomized rTMS group
 - Confidence rating
- Visits 4 & 5: Complete randomized task alone & again with opposite rTMS group
 - Confidence rating
- MRI probes: in the scanner, participant completes randomized task alone & then with TMS probe.

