3.1 Primary Objective

We will determine both an “intensity (difficulty) effect” and an “emotion effect” of task-induced fMRI activity in the scanner, collecting these measures in the same subjects. Participants will receive two working memory tasks:

1a) Sternberg Sorting Task (SST): a cognitive task comparing low-load vs. high-load conditions in which the picture stimuli are letters.

1b) International Affective Picture System (IAPS): an emotional task using IAPS picture that will also compare low load and high load conditions. The number of images will vary by condition load, but for both the high-load & low-load conditions, participants will look at IAPS pictures and answer questions about the images. Further, jittered within this design will be both neutral and negative blocks of IAPS pictures.

We will compare low-load vs. high-load brain activation and connectivity in the cognitive vs. emotional tasks.

Hypothesis 1a: Compared with the maintenance (low-load) SST condition, the high-load cognitive SST condition will produce greater DLPFC activation and dIPFC/sgACC anticorrelation.

Hypothesis 1b: Compared with the low-load IAPS emotional task, the high-load IAPS emotional pictures will produce higher activity in the DLPFC and dIPFC/sgACC anticorrelation.

Hypothesis 1c: The picture rating for arousal will be correlated with the activity in the DLPFC and dIPFC/sgACC anticorrelation.

Secondary Objectives:

Aim 2: to determine which task provides greater augmentation of the TMS-induced DLPFC activation, participants will receive in randomized order:

- 1) The cognitive SST working memory task or the IAPS task alone
- 2) rTMS + the cognitive SST working memory task or rTMS + the IAPS emotional task in randomized order. rTMS and the cognitive tasks will be conducted in the fMRI scanner where brain activation to a TMS probe and connectivity will be obtained.
- 3) rTMS alone

Hypothesis 2a: rTMS + either task will have greater DLPFC activation and greater dIPFC/sgACC anticorrelation than rTMS alone.

Hypothesis 2b: rTMS + the IAPS emotional working memory task will have greater DLPFC activation and greater dIPFC/sgACC anticorrelation than rTMS + cognitive SST (more robust)

Hypothesis 2c: rTMS + IAPS emotional task will have greater signal to noise (more selective).

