Aim 3: to determine the effect of neuromodulation on DLPFC activation healthy participants will be randomized to one of the 3 task conditions: high-load cognitive SST, high-load IAPS task, or low-load SST (sham task condition). Following a 4 session course (2 session separated by at least 4 hours on one day, followed by 2 sessions separated by at least 4 hours on a second day) of either active rTMS or sham TMS neuromodulation in combination with the task condition participants will again have probe sessions in the scanner where DLPFC activation and connectivity will be determined. Following a 2-week interval, participants will receive the other stimulation condition (sham TMS if active first and active TMS if sham first).

[figure not shown]
Hypothesis 3a: Task (any of the 3) + active rTMS will result in greater DLPFC activation and greater dIPFC/sgACC anticorrelation than task plus sham rTMS

Hypothesis 3b: the IAPS task in combination with active rTMS will produce greater activation than the cognitive SST + active TMS or than control task + active TMS.

CONFIDENTIAL

4 Investigational Plan

Below is an example of the proposed study flow after screening visit. Please refer to attached task descriptions for further information:

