4.1 General Design

A mechanism oriented study, with within subjects design will be used. Healthy volunteer participants who are between 18 – 60 years old and meet basic eligibility criteria, will be offered participation in this study. Consenting participants will then undergo a baseline MRI scan in order to identify the exact location of the “Fitzgerald Target” in their DLPFC. Study staff will use FSL to analyze the images and communicate the coordinates via BrainSight to study coordinators. Participants will complete within subject comparisons and then will be randomized to a 3 arm study.

In the first phase participants will complete:

- 1) low-load condition vs high-load condition in the (cognitive) SST
- 2) low-load condition vs high-load condition in the (emotion) IAPS task

They will then complete again (in randomized order) with rTMS:

- 1) rTMS alone
- 2) rTMS + SST (cognitive)
- 3) rTMS + IAPS (emotion)

rTMS and the cognitive tasks will be conducted in the fMRI scanner where brain activation to a TMS probe and connectivity data will be obtained.

Finally they will be assigned to one of 3 groups to determine the effect of neuromodulation on DLPFC activation. Healthy participants will be randomized to one of 3 task conditions: high-load SST, high-load IAPS or low-load SST (sham task). Following a 4 session course of either active rTMS or sham rTMS neuromodulation (both active rTMS & Sham rTMS: at 120% RMT in triplet 50 Hz bursts, repeated at 5 Hz; 2 s on and 8 s off; 600 pulses per session; for a total duration of 3 min. and 9 s) in combination with one of

CONFIDENTIAL

the 3 task conditions participants will again have single pulse probes (120% RMT; 77 pulses/session) sessions in the scanner where DLPFC activation and connectivity will be determined. In this protocol we will use anatomically guided rTMS alone or in combination with tasks to test the hypothesis that cognitive paired associative stimulation results in augmented cortical response.

5 Study Population and Duration of Participation

25 healthy adults between the ages of 18 – 60 who meet inclusion/exclusion criteria will be asked to participate in approximately 7 study visits over the course of 3 – 4 weeks.

We estimate the following amount of time for each visit:

- Screening Visit: 2 hours
- Visit 1 - Baseline MRI Scan: 1 hour
- Visit 2 – Initial Task MRI Scan: 2 hours
- Study Visits 3 – 5: 2 hours each
 - Includes 1 hour MRI scan after Visit 4

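### Sections 6.2.1–6.2.3 leave out the rTMS-alone run that the design sections list and that Hypothesis 2a needs as its comparator

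*Combined protocol and SAP*

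**What the plan says.** The visit-level text is in Section 6.2. For the scan before randomisation, Section 6.2.1 gives "tasks in the scanner with TMS". Section 6.2.2 provides for "Randomized order of learning all 3 study tasks (SST, IAPS, and Sham) in the scanner without TMS" ahead of the baseline scan. Section 6.2.3 then says that at Visit 1 "in the scanner participant completes all 3 tasks, in previously randomized order with TMS". Section 6.2.4 places randomisation to task and stimulation after that visit. For the later scans, the neuromodulation and probe block (numbered 5.2.5, although it sits under 6.2) says: "MRI probes: in the scanner, participant completes randomized task alone & then with TMS probe".

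The sham task is defined under Aim 3 in Section 3.1, where the three task conditions are "high-load cognitive SST, high-load IAPS task, or low-load SST (sham task condition").

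The design text differs. Section 4.1 introduces the second set of runs with "They will then complete again (in randomized order) with rTMS" and lists rTMS alone, rTMS + SST and rTMS + IAPS, all before assignment to the three groups. The opening of Section 6 gives the same three. The Aim 2 text, in the Study Summary and again in Section 3.1, also lists rTMS alone. Hypothesis 2a in Section 3.1 reads: "rTMS + either task will have greater DLPFC activation and greater dIPFC/sgACC anticorrelation than rTMS alone".

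**The concern.** Hypothesis 2a asks whether adding a task raises the response to TMS above the response to TMS by itself. That needs a run with TMS and no task in the same participants. The general sections provide one. The only text that sets out the procedures visit by visit does not.

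The omission would be easy to miss on the day. Both lists have three entries, so a coordinator working from Sections 6.2.2 and 6.2.3 would complete a full three-run session with nothing apparently absent. Section 6.2.3 also relies on an order randomised earlier. The only earlier order in Section 6.2 is the one for learning three tasks without TMS, and a TMS-alone run has no place in it.

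At stake is the comparator for one secondary hypothesis. Aim 2 is a within-participant comparison, so every participant scanned under the literal Section 6.2 text would be affected.

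**Working it through.** The plan states no figure on this point, so the check is a comparison of the texts.

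**Step 1. Conditions with TMS in the scanner before randomisation.**

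| Condition | Section 4.1 and opening of Section 6 | Sections 6.2.2–6.2.3 |
|---|---|---|
| SST with TMS | listed | listed |
| IAPS with TMS | listed | listed |
| TMS, no task | listed | not listed |
| Sham task with TMS | not listed | listed |

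Each list has 3 conditions and 2 are common, so 3 − 2 = 1 differs. The Aim 2 text in the Study Summary and Section 3.1 agrees with the left-hand column on rTMS alone but does not itself fix when the run takes place.

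**Step 2. Can the sham task serve as TMS alone?** No. It is low-load SST, a task the participant performs. Write the responses as R(TMS), R(TMS + high-load) and R(TMS + low-load). Using the sham run as the reference gives

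R(TMS + high-load) − R(TMS + low-load) = [R(TMS + high-load) − R(TMS)] − [R(TMS + low-load) − R(TMS)].

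That is a difference between two task effects, whereas Hypothesis 2a concerns the first bracket alone.

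**Step 3. Can TMS alone be recovered from task-alone and task-with-TMS runs?** Only by taking R(TMS) = R(TMS + task) − R(task). This assumes that task and TMS responses simply add, and whether they do is what an augmentation study sets out to learn.

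**Step 4. Does another described scan supply the run?**
- Baseline scan: Section 6.2.1 says there is no TMS probe.
- Pre-randomisation TMS scan: three tasks with TMS (Section 6.2.3).
- Later probe scans: the randomised task alone, then with the probe. The natural reading of the second part is the task together with the probe.
- Screening: test TMS is given for tolerability, outside any scan.
- Schedule table in Section 6: marks behavioural tasks and TMS at Visit 2 but names no conditions, so it does not settle the matter.

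Section 6.2 has 3 lines that describe TMS in the scanner (6.2.1 for Visit 1, 6.2.3, and the probe line). None names TMS alone.

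**Step 5. Visit numbering.** Section 6.2.3 calls this scan Visit 1. The schedule table marks no TMS at Visit 1 and marks TMS, tasks and MRI at Visit 2, the initial task scan. I therefore take Visit 1 in Section 6.2.3 to be Visit 2 in the table. Section 6.2 also puts neuromodulation at Visits 2–3 and 4–5, where the visit list in Section 5 has Visits 3–5 and 6–8.

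**Step 6. Effect on the hypotheses.** Hypothesis 2a loses its reference run. Hypothesis 2b compares rTMS + IAPS with rTMS + SST, and both runs are in both lists.

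**The case against.** The best defence is that the run is in the plan, and in the same section. The opening of Section 6 lists rTMS alone, in randomised order, before group assignment. Section 6.2 is a short bullet list that omits the run without excluding it. The harm arises only if staff follow the bullets and disregard the text above them. This stands as a limit on how likely the loss is. It does not remove the contradiction, because Section 6.2 gives a complete-looking alternative set of three rather than an abbreviated version of the same set.

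A second defence is that Section 6.2 cannot be run against the schedule without renumbering visits, so the missing run is one symptom of a section that was not aligned with the rest. That is fair, and the fix covers it.

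Third, Section 4 points to a study-flow figure and to attached task descriptions, neither of which was available. Either may set out the runs and their order. That also stands. If they do list rTMS alone, Section 6.2 would still disagree with them.

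A reader might infer that four separate statements require rTMS alone. They are two near-duplicate pairs: the Aim 2 text appears twice, and Section 4.1 and the opening of Section 6 are close copies.

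**Conclusion.** The point holds as an inconsistency between the visit-level procedures and the design text. One of three conditions at the pre-randomisation TMS scan differs. Followed literally, Section 6.2 leaves Hypothesis 2a, one secondary hypothesis, without a comparator, and Hypothesis 2b intact. It should be corrected. Confidence is moderate because of the unseen figure and attachments and the assumed visit mapping.

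Two stronger readings are tempting and are not supported:

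- That the trial will acquire no rTMS-alone data at any scan. A count over every scan would need the visit mapping above, would need the probe line to cover the scan before Visit 6, and would treat an omission as a prohibition. Section 5 also implies five scans (Visits 1 and 2, after Visit 4, before Visit 6, after Visit 8), while the schedule table marks MRI in four columns. What can be said is that no scan in the available text clearly acquires the run if Section 6.2 is taken literally.
- That Aim 2 as a whole fails. Hypothesis 2b keeps both runs. Hypothesis 2c names no comparator, but it follows 2b in parallel form, so it cannot be counted as lost.

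**What to change.** Reconcile Sections 6.2.1–6.2.3 with the Aim 2 text (Study Summary and Section 3.1), Section 4.1 and the opening of Section 6. The randomised run list for the pre-randomisation TMS scan should explicitly name the rTMS-alone run that Hypothesis 2a requires. It should also say how that run enters the randomised order, since the order in Section 6.2.2 covers tasks only. The sponsor should state whether the sham-task run with TMS stays in that scan.

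In the same edit, align the visit numbers in Section 6.2 with the visit list in Section 5 and the schedule table in Section 6.

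The cost is a wording edit. If the sponsor keeps the sham-task run as well, the scan gains one run, which would have to fit the 2 hours that Section 5 allots to Visit 2. No number of pulses or other stimulation setting is proposed here.

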- 7 – 14 day break pending participant availability
- Study Visits 6 – 8: 2 hours each
 - Includes 1 hour MRI scans before Visit 6 and after Visit 8

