5.5 Total Number of Subjects and Sites

We plan to initially enroll 25 healthy control patients at the University of Pennsylvania.

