5.6 Vulnerable Populations: N/A

6 Study Procedures

A mechanism oriented study, with within subjects design will be used. Healthy volunteer participants who are between 18 – 60 years old and meet basic eligibility criteria, will be offered participation in this study. Consenting participants will then undergo a baseline MRI scan in order to identify the exact location of the “Fitzgerald Target” in their DLPFC. Study staff will use Brain Site to analyze the images and communicate the coordinates to study coordinators. Participants will complete within subject comparisons and then will be randomized to a 3 arm study.

In the first phase participants will receive:

- 1) a low load condition vs a high load condition in the SST
- 2) a low load condition vs a high load condition in the IAPS task

They will then receive in randomized order:

- 1) rTMS alone
- 2) rTMS + the SST or
- 3) rTMS + the IAPS task in randomized order.

rTMS and the cognitive tasks will be conducted in the fMRI scanner where brain activation to a TMS probe and connectivity data will be obtained.

Finally they will be assigned to one of 3 groups to determine the effect of neuromodulation on DLPFC activation. Healthy participants will be randomized to one of 3 task conditions: high-load SST, high-load IAPS or low-load SST (sham task). Following a 4 session course of either active iTBS or sham TMS neuromodulation (both iTBS & Sham: at 120% RMT in triplet 50 Hz bursts, repeated at 5 Hz; 2 s on and 8 s off; 600 pulses per session; for a total duration of 3 min. and 9 s) in combination with one of the 3 task conditions participants will again have single pulse probe (120% RMT; 77 pulses/session; 2.4 s each) sessions in the scanner where DLPFC activation and connectivity will be determined. In this protocol we will use anatomically guided TMS alone or in combination with tasks to test the hypothesis that cognitive paired associate stimulation results in augmented cortical response.

Although there are no known risks related to MRI on pregnant women or a fetus, there is a possibility of yet undiscovered pregnancy related risks. Since there is no possible benefit from participating in this protocol for a pregnant woman, we will exclude pregnant women. All women of child bearing potential are asked if they are using a reliable method of birth control and are required to attest that they are not pregnant before study visit and on the TMS safety screening form.

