7.7 Safety Evaluations

The primary investigator will routinely monitor and evaluate study procedures for potential increased risk.

8 Statistical Plan

Efficacy within subjects: Repeated measures ANOVA will be used to assess changes from baseline to post-stimulation for each task condition.

Efficacy between subjects: neuro-response rates and time to response will be compared with published rates within the literature to extrapolate the significance of this modality.

9 Safety and Adverse Events

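### No balancing is specified for the six task-by-order combinations (about four people each) and no period term is planned; under simple randomisation a task arm with a 3:1 or worse stimulation order is about as likely as not

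*Combined protocol and SAP*

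**What the plan says.** - **Assignment.** Section 6.2.4 states that, after Visit 1, participants are "Randomized to SST task only, IAPS task only, or Sham task only & either Active rTMS + task or Sham rTMS + task".
- **Crossover.** Section 3.1, Aim 3, adds: "Following a 2-week interval, participants will receive the other stimulation condition". The second randomised factor is therefore the order of active and sham.
- **Sample size.** Section 5.5: "We plan to initially enroll 25 healthy control patients at the University of Pennsylvania".
- **Allocation method.** Sections 3.1, 4.1, 6 and 6.2.4 use the word randomised and add nothing about ratio, blocking, stratification, minimisation, list generation or concealment.
- **Analysis.** Section 8: "Repeated measures ANOVA will be used to assess changes from baseline to post-stimulation for each task condition". It names no period, sequence or carryover term.
- **Between-arm hypothesis.** Hypothesis 3b expects that "the IAPS task in combination with active rTMS will produce greater activation than the cognitive SST + active TMS", and likewise in comparison with the control task. Hypothesis 3a pools all three tasks.
- **Second-course baseline.** The visit list in section 5 has an MRI scan before Visit 6 as well as after Visit 8. The procedure table in section 6 marks no MRI at Visits 6 and 7. Section 6.2 numbers the visits differently and ties the MRI probes to no visit.
- **Break between courses.** Aim 3 gives two weeks. Section 5 gives "7 – 14 day break pending participant availability".

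**The concern.** In a two-period crossover, each person's active-minus-sham difference also contains the difference between course 1 and course 2, with a sign that depends on the order received. It cancels in the arm mean only if the two orders are equally frequent in that arm, or if the model carries a period term. The plan secures neither.

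A course difference is plausible. Each participant repeats the one assigned task, alone and with stimulation, at every neuromodulation visit, so the scan after course 2 follows roughly twice the post-assignment task exposure of the scan after course 1. With about eight people per task arm, chance alone can make order lopsided in one arm and even in another. The per-task results would then carry different amounts of the course difference, and a comparison between tasks (Hypothesis 3b) would partly be a comparison of orders.

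**Working it through.** The plan gives no power calculation and no allocation ratio, so it has no figure to reproduce.

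**1. Size of the combinations.** N = 25 (section 5.5), 3 tasks, 2 orders. 25/3 = 8.33 per task arm; 25/6 = 4.17 per combination.

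**2. Chance of a lopsided arm.** Assumption: simple randomisation to six equally likely combinations. Arm sizes are multinomial (25; 1/3 each) and, within an arm of n, the number active-first is binomial (n; 1/2). Exact summation gives:

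| Event | N = 25 | N = 24 | N = 20 |
|---|---|---|---|
| At least one arm 3:1 or worse | 0.493 | 0.515 | 0.614 |
| At least one arm 2:1 or worse | 0.815 | 0.827 | 0.878 |
| Some combination has 0 or 1 person | 0.348 | 0.396 | 0.633 |
| Some combination is empty | 0.062 | 0.075 | 0.152 |

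Check on the empty combination at N = 25: 6 x (5/6)^25 - 15 x (4/6)^25 = 0.0629 - 0.0006 = 0.062.

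**3. Other schemes that fit the text.**
- Arms fixed at 8/8/8, order by coin flip. One arm: P(6:2 or worse) = 2 x (28 + 8 + 1)/256 = 0.289. At least one of three: 1 - 0.711^3 = 0.641.
- Arms fixed at 8/8/9. For the arm of 9: P(7:2 or worse) = 2 x (36 + 9 + 1)/512 = 0.180. At least one: 1 - 0.711^2 x 0.820 = 0.585.
- Separate blocked lists, task in blocks of 3 and order in blocks of 2 (40,000 simulated trials): about 0.45. Balancing each factor alone does not balance order within task.

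**4. What a lopsided arm does.** Let the true effect be t, the course-2-minus-course-1 difference p, and the arm have a active-first and b sham-first (n = a + b). Active-first people show t - p and sham-first people t + p, so the unadjusted arm mean is t + p(b - a)/n. If a period term is fitted from that arm's data alone, efficiency relative to an even split is 4ab/n².

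| Order split | Share of p in the unadjusted contrast | Efficiency with the arm's own period term |
|---|---|---|
| 5:4 | 1/9 = 0.11 | 80/81 = 0.99 |
| 5:3 | 2/8 = 0.25 | 60/64 = 0.94 |
| 6:2 (3:1) | 4/8 = 0.50 | 48/64 = 0.75 |
| 7:1 | 6/8 = 0.75 | 28/64 = 0.44 |
| 8:0 | 1.00 | not estimable |

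The documents give no value for p, so leakage can only be stated as a fraction of it.

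**5. Hypothesis 3b.** With s the active-first share in an arm, two arms compared on active-condition scans differ by p times the gap in s; compared on active-minus-sham, by 2p times the gap. In 400,000 simulated draws at N = 25, the gap between a given pair of arms averages 0.21 and is 0.25 or more in 35% of draws. Between the two most different arms it averages 0.31 and is 0.25 or more in 61%.

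**6. Hypothesis 3a.** Pooled over 25 people, a 3:1 or worse split means 19:6 or worse, with binomial probability about 0.015. A split of 2:1 or worse (17:8) has probability 0.108.

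**7. Joint blocking.** Four full blocks of 6 give 4 per combination and the 25th person makes one of them 5: arms 8/8/9, worst split 5:4, P(3:1 or worse) = 0. With block sizes of 6 and 12 drawn at random (20,000 simulated trials), the largest within-arm order difference was 1 in 89% and 2 in 11%, never more, and arms were 8/8/9 in 86%.

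**8. Predictability.** With fixed blocks of 6 and known past allocations, the best guess of order is right for 4.1 of 6 people on average: 4.1/6 = 68%, against 50% under simple randomisation.

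**The case against.** The strongest reply is that silence about the method is not evidence of a bad one. Blocked or minimised allocation fits the word randomised just as well, and the study-flow figure is not visible. That stands: a reader might infer that the trial uses no balancing, and the documents do not say so. Every probability above is conditional on an assumed scheme. Nor does the indivisibility of 25 by 3 or 6 leave the numbers to chance, since blocking gives 4 or 5 per combination. What remains is that simple randomisation would comply with the plan as written.

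Second, the 50% leakage belongs to an unadjusted active-minus-sham contrast. Section 8 speaks of change from baseline. If a fresh scan before course 2 is that course's baseline, any practice or habituation already present by then is subtracted, and only a difference between courses in the within-course change leaks. This stands in part, because section 5 and the section 6 table disagree on whether that scan exists. Sections 6.2.2 and 6.2.3 also have everyone perform all three tasks before assignment, so some practice precedes both courses.

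Third, it is tempting to say that in a single-order arm no analysis can separate stimulation from course. That holds only for the arm's own data. A model with one course effect common to all three arms can separate them, if that common effect is believed. An empty combination is also a 6% event, not a 49% one.

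**Conclusion.** The point holds as a gap in design and analysis that can be closed before enrolment. The plan sets no balancing for six combinations of about four people and no period term to correct an imbalance. Under simple randomisation, at least one task arm has a 3:1 or worse order split in about 49% of trials; fixed arms with a coin flip for order give 59% to 64%, and separately blocked lists about 45%.

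The consequence depends on there being a real difference between courses, whose size the documents do not give, and on which scan serves as the second-course baseline. It falls on the per-task results and Hypothesis 3b. A reader might infer that the whole crossover is compromised; the 1.5% chance of a 3:1 split over all 25 people does not support that for Hypothesis 3a.

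**What to change.** 1. **Section 6.2.4:** assign task and order jointly from one concealed list, in permuted blocks over the six combinations, prepared before enrolment and withheld from staff who enrol or assess. Blocks of 6 give the tightest balance; undisclosed or varying sizes of 6 and 12 are harder to predict and slightly looser.
2. **Section 8:** add a period (course) term to the repeated measures model, and state whether it is common to the three tasks or fitted per task.
3. **Sections 3.1, 5, 6 and 6.2:** reconcile whether there is a scan before the second course, the visit numbering, and the length of the break; then state in section 8 which scan is the baseline for each course.

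**Cost.** No extra participants or visits are needed for items 1 and 2. It would be wrong to call blocking free, however: fixed blocks of 6 raise the chance of guessing order from 50% to about 68% if past assignments become known, which matters at a single site in a study described as double-blind. Blocking also balances people assigned, not completers. Section 6.5 expects some withdrawals, no replacement rule is given, and the 25 are counted at enrolment while assignment comes after Visit 1. The period term is therefore needed even with blocking. Neither change removes carryover from the first course.
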